 - xi. Procedures for safe and orderly termination if the participant wishes to withdraw
 - xii. A detailed explanation of all potential risks, including unforeseen risks, and potential benefits
 - xiii. Remuneration
- b. **Protections Against Risk.** As described above, we will exclude from enrollment individuals who are at increased risk for adverse events resulting from study medications. We will screen for side effects of study medications weekly, and monitor for biochemical side effects through laboratory screening. Individuals who have serious adverse reactions will have study participation terminated. Risk associated with the outpatient screening and checkup visits (phlebotomy) is minimal. Risk associated with inpatient procedures (the EDD and RPF studies) will be minimized by continuous monitoring by a physician (the PI or Co-investigator) and nurse, and – as noted – participants will already be hospital inpatients at that time so any serious adverse events can quickly be addressed. No vulnerable populations will be enrolled.

Potential Benefits

Potential benefit to society: As described in detail in the **Study Procedure** section, we will perform a small pilot study of obese individuals. We plan to enroll a total of 20 individuals into a randomized controlled trial. All participants will be adults (age \geq 18 years), and will be recruited from the Boston area. Volunteers will be recruited and screened for inclusion based upon having a BMI \geq 30 kg/m², and having HbA1C between 5.7 and 6.4%. Other than having these “conditions”, potential participants will be expected to otherwise be in general good health, without severe co-morbid conditions as described in the **Subject Enrollment** section. There will be no involvement of special vulnerable populations. After randomization, participants will be retained by weekly phone calls; additionally, the duration of this trial (6 weeks) is relatively short. Study group assignment will be random, of the 20 participants, 10 will receive placebo, and 10 will receive controlled release melatonin (2.0mg of Circadin[®] nightly for 6 weeks). The 2 mg controlled-release formulation of melatonin has been studied previously in diabetic subjects and improves sleep duration. Pharmacokinetic data suggests that this dose of melatonin achieves nocturnal serum melatonin levels at or above physiological concentrations among healthy volunteers and is therefore adequate to replete nocturnal melatonin in individuals who have relatively low endogenous secretion.

The key potential benefit is the knowledge that is gained on potentially modifiable mediators of important pathophysiologic mechanisms of disease. The segment of the US population that would meet our study criteria is large; specifically, over half of the US adult population is obese, and nearly a quarter of these individuals have pre-diabetes. Thus, the results of this study could have profound public health implications.

Potential benefit to participants: It is possible that participants will gain direct benefit from these studies. First of all, it is possible that individuals who are not randomized to placebo will benefit from treatment. On the other hand, because this study is only 12-weeks in duration, these benefits (if present) will likely be short-lived.

Monitoring and quality assurance

We will submit our data safety monitoring plan (DSMP) to the Brigham and Women's Hospital Institutional Review Board for approval. It is based upon the guidelines set forth by the Brigham and Women's IRB that we have formulated our Safety Monitoring Plan.

a. Type of DSMP. We plan to implement a fully independent data safety monitoring board (DSMB), which will meet every 6 months. The DSMB will have 2 members independent of Drs. [name] and [name]; a statistician and a clinical investigator. The first meeting will be prior to subject enrollment to allow agreement on expectations of investigator and DSMB, with review of the study protocol approved by IRB. Safety data regarding adverse effects will be presented at each DSMB meeting as will unblinded outcome data. At each meeting the DSMB will decide on the continuation of the trial after considering the study risk based on the accumulation of adverse events and the futility of the trial based on the outcomes data. In addition to the DSMB a committee of investigators, including Drs. [name] and [name], as well as a research pharmacist will provide safety monitoring on a weekly basis allowing "on-the-spot" monitoring for abnormal safety labs or protocol breaches as well as providing decisions regarding termination of an individual's participation. This will allow greater flexibility and speed to react to safety issues should they arise.

b. Data to be reviewed. The safety committee made of investigators will review data pertaining to side effects and adverse events.

ClinicalTrials.gov Requirements

The principal investigator of this proposal, as the responsible party, will comply with Public Law 110-85 (FDAAA), and will register this clinical trial on ClinicalTrials.gov.

References:

1. EU. *Fifth European Working Conditions Survey*. Luxembourg: Publications Office of the European Union; 2012 2012.
3. Bixler E. Sleep and society: an epidemiological perspective. *Sleep Med*. Sep 2009;10 Suppl 1:S3-6.

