While others have shown that exposure to light at night during shift work depresses nocturnal melatonin secretion (the chief hormonal output from the central circadian pacemaker),^{37,38} we have found that individuals with decreased nocturnal melatonin secretion at baseline have a significantly increased risk of later developing type 2 diabetes^{39,40} and cardiovascular disease (unpublished work), both important risk factors for the development of CKD (**Table 1**).

Table 1: Odds Ratio for incident type 2 diabetes and myocardial infarction according to nocturnal melatonin secretion		
	Odds Ratio (per decrease in log [urine melatonin/creatinine])	
	Type 2 diabetes	Myocardial infarction
Crude	1.36 (1.14-1.61)	1.51 (1.16-1.96)
Adjusted	1.48 (1.11-1.98)	1.69 (1.14-2.51)

Less nocturnal BP dipping is related to poor sleep efficiency⁴¹ and short sleep duration.⁴² We therefore analyzed the association of decreased nocturnal dipping with incident CKD among individuals recruited from the Jackson Heart Study and found that decreased dipping was associated with an increased risk of incident CKD (**Table 2**)⁴³.

Table 2: Odds Ratio of incident CKD according to nocturnal dipping	
	Nocturnal dipping (per 10% of awake SBP)
Unadjusted (N = 603)	0.58 (0.42 – 0.79)
Adjusted (N = 408)	0.55 (0.32 – 0.96)

These results, in addition to work by others (see, Background and Significance) suggest that changes in an individual's sleep-wake cycle lead to disruption of normal diurnal regulation of physiological processes, potentially promoting the development of CKD. Thus, we analyzed the association of short self-reported sleep duration with longitudinal changes in eGFR among women enrolled in the Nurses' Health Study and demonstrated that individuals who had lower sleep duration had faster declines in eGFR and higher odds of albuminuria (unpublished results, **Tables 3&4**), further supporting the hypothesis that circadian disruption is detrimental to renal function.

Sleep duration	Unadjusted	Adjusted
≤ 5 hours	1.64 (1.14-2.37)	1.54 (1.05-2.27)
6 hours	1.23 (1.03-1.46)	1.17 (0.97-1.41)
7-8 hours (ref)	1.0 (ref)	1.0 (ref)
9 hours	0.89 (0.59-1.34)	0.73 (0.47-1.14)
≥ 10 hours	1.38 (0.45-4.25)	1.00 (0.31-3.19)

Sleep duration	Unadjusted	Adjusted
≤ 5 hours	2.31 (1.42-3.79)	2.12 (1.26-3.55)
6 hours	1.36 (1.02-1.81)	1.30 (0.96-1.76)
7-8 hours (ref)	1.0 (ref)	1.0 (ref)
9 hours	1.00 (0.51-1.93)	0.86 (0.42-1.76)
≥ 10 hours	2.15 (0.48-9.59)	1.33 (0.26-6.74)

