We will recruit individuals from the Boston area who meet the inclusion and exclusion criteria listed in **Table 5**. Recruitment will take place through several venues. First, we will recruit from those who have already completed our MODERATE randomized trial (N>200 who have completed so far). The vast majority these individuals still reside in Boston. MODERATE participants have provided consent to be re-contacted for future studies. We will use the MODERATE database to identify individuals who may be eligible for our study, and contact them directly to invite them to participate.

Second, we will simultaneously attempt to enroll study participants who fulfill the age and BMI requirements using routine media outlets in the local community and also online advertising. These include: (1) billboards placed in Boston mass-transit buses and subways; (2) advertisements in local print media, such as the Boston Metro and the Boston Globe; (3) online advertisement with websites such as Craig's List and Oodle (these sites have been productive sources for recruitment in the past).

Third, we will use recruitment opportunities provided through Partners, such as Partners RSVP, and ClinicalTrials@Partners.

We will include both men and women and all races and ethnicities. The only exception will be women who are pregnant because certain medications used during the inpatient evaluations (e.g., nitroglycerine), and certain study medications (i.e., captopril) are contraindicated during pregnancy.

Table 5. Eligibility Criteria

Inclusion Criteria

- BMI ≥ 30 kg/m²
- Age ≥ 18 years
- HbA1c 5.7-6.4%
- Self reported sleep <7 hours per night

Exclusion Criteria

- Current or prior history of diabetes mellitus
- Use of hypoglycemic meds or random serum glucose ≥ 200 mg/dL
- Estimated GFR <60 mL/min/1.73m²
- Inability to extend sleep by 1 hour per night
- Pregnant or breast-feeding
- Preexisting lung disease requiring oxygen

- Preexisting CVD
- Active or uncontrolled psychotic disorder
- Active or uncontrolled bipolar illness
- Active malignancy within the prior 5 years
- Use of antihypertensive meds
- Hepatic impairment
- Job requires rotating night shifts
- Bariatric surgery within the prior 12 months
- Use of hypnotic meds
- Hematocrit <36%(women) or <41% (men)
- Use of natural sleep aids
- Known allergy/intolerance of ACE inhibitors
- History of stroke
- Recent (within 2 weeks of study) or upcoming travel across time zones

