- Known obstructive sleep apnea or use of continuous positive airway pressure
- Insomnia
- Known allergy to melatonin
- Hypertension Type 1 or 2 (BP >150/90)
- Lactose Intolerance
- Autoimmune Disease

[figure not shown]
Subject Enrollment

Responders to advertisements will be pre-screened by telephone to obtain a BMI estimate and a medical history to gauge potential eligibility (**Table 5**). For those who may be eligible following this phone query, the basic study schema (**Figure 1**) will be described to identify those who remain interested in participation after learning the duration, inpatient requirements, and potential medication use. These individuals will then be invited to attend an outpatient screening visit.

We anticipate that the sex and race/ethnicity breakdown of subjects enrolled into EMC-PILOT will be similar to that which we have experienced in the MODERATE trial. Thus far in the MODERATE trial, enrolled subjects are 63% female, 28% black, 7% more than one race, and 13% Hispanic.

The pilot study is a double-blind, placebo-controlled randomized trial, in which 16 subjects with obesity (BMI \geq 30 kg/m²), pre-diabetes (HbA1C, 5.7-6.4%), and self-reported short sleep duration (<7 hours/night) are randomly assigned 1:1 to receive either placebo or 2 mg of controlled-release melatonin, taken orally every evening 1 hour before bed for 6 weeks. **All subjects will be asked to extend their sleep time by one hour** during the 6 week period between inpatient visits. Endpoints will be measured at both the baseline and 6-week inpatient visits.

Figure 1: Schema for pilot study with sleep extension and nightly melatonin as treatments.

Screening Visit: Screening visits will take place at the Brigham and Women’s Outpatient Center for Clinical Investigation (CCI; [name]). During the outpatient screen, [name] will explain the study in detail, review the consent form, and answer questions. After obtaining written informed consent for participation, a history and physical examination will be performed in order initially judge eligibility based upon the criteria set out in **Table 5**. Those individuals deemed potentially eligible based upon the screening history and exam will undergo phlebotomy and analysis for HbA1c, serum chemistries and glucose, and CBC to confirm eligibility using the criteria presented in the table.

[figure not shown]
Study Procedures

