Pre-admission: All participants will wear a wrist activity monitor for a total of 8 weeks; 2 weeks prior to the baseline inpatient visit and for the 6 weeks between inpatient visits, **Figure 2**. They will complete a daily sleep log during the 2 weeks preceding the baseline visit and 6 weeks preceding second visit. Three days before admission, participants will be placed on a high salt diet by supplementing their usual diet with 150 mmol sodium/day for 3 days using dry bouillon added to food. All participants will also be asked to do a 24 hour diet recall for the day before admission.

Treatment assignments: Prior to admission for the baseline visit, **subjects will be randomized (1:1)** to receive study medication (melatonin 2mg of controlled release formulation or placebo). **All subjects will be asked to extend their sleep time by one hour** during the 6 week period between inpatient visits.

Baseline and Follow-up inpatient visit: Baseline and 6-week inpatient visits will be virtually identical. Each inpatient visit will begin at 4:00PM on Day 0 and end at 4:00PM on Day 1, **Figure 2**.

Figure 2: Schema for inpatient visit studies at 6-week visit.

Day 0 — We will complete two 12-hour urine collections for each subject. All subjects will begin the first 12-hour urine collection at their home at 7:00AM on day 0 of admission to the Brigham and Women’s Hospital Center for Clinical Investigation (CCI). The first 12-hour urine collection will be ended at 7:00PM that evening. The second 12-hour collection will begin and continued overnight until 7:00AM on day 1. The nurses will keep the daytime (7AM to 7PM) and nighttime (7PM to 7AM) urine separate to permit analysis of diurnal variation in urinary analytes. Subjects will fast after 9 pm to ensure a 12-hour fast by the next morning.

[figure not shown]

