Ambulatory blood pressure monitor – The device, the SPACELABS Inc. 90207, consists of a 4.5" x 3.4" x 1.1" box weighing 12 oz. that is usually worn on the belt or pant/skirt-line, and a chord that connects the box underneath the clothing to the cuff which is worn on the upper arm. Multiple cuffs of various sizes (small 17-26 cm, standard 24-32 cm, large 32-42 cm, and extra large 38-50 cm) will be available and the appropriate cuff for each participant will be utilized. Once affixed, the device is switched on and the study coordinator will manually initiate two or three readings so that the participant may become accustomed to how the monitor works/feels before he/she leaves the CCI. The monitor will be pre-

programmed to record the BP every 30 minutes during the day and every 60 minutes at night. Instructions to participants will include removal of the device before bathing/showering to keep the device dry. At the end of the 24hr monitoring period, the participant will switch off the device and mail it back to the study coordinator in a pre-paid mailer (which will be provided prior to CCI discharge). Once received, the study coordinator will download the data using SPACELABS Inc. 92506 Report Management System (a PC-compatible Interface).

Data Collection:

This study will collect demographic information (age, self-described race and ethnicity, sex), and physical data (height, weight, screening blood pressure). Blood and urine samples will be analyzed for various biomarkers to collect the data necessary to carry out the specific aims, as described in the section above *Parameters Measured*. All of these data will be recorded in association with a study ID number, and kept as secure excel files by the statistician and programmer. The only individually identifiable private data that will be collected are names, addresses, and contact phone numbers so that participants can be screened with follow-up phone calls, and they will be admitted to the inpatient CCI under their name. This personal information, however, will not be associated with the results obtained from the various tests performed, as the latter will be associated with a study ID number. The file linking the study ID number and the personally identifiable information will be kept by the PI in a secure location and will not be violated unless it becomes medically necessary to contact a participant on the basis of one of their lab screening tests (e.g., elevated liver function tests).

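### Table 5 excludes only rotating night-shift jobs, so a fixed night worker who sleeps under 7 hours by day is eligible, although dosing and the day/night measures presuppose sleep at night

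*Combined protocol and SAP*

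**What the plan says.** **Eligibility (Table 5).** The work-schedule exclusion is "Job requires rotating night shifts". The sleep inclusion criterion is "Self reported sleep <7 hours per night", with no clock time attached. The nearest related exclusions are "Inability to extend sleep by 1 hour per night" and "Recent (within 2 weeks of study) or upcoming travel across time zones". The other sleep-related items cover insomnia, known sleep apnea or CPAP, hypnotics and natural sleep aids. None says when the sleep period must fall.

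**Dosing (Subject Enrollment).** Study drug is "taken orally every evening 1 hour before bed for 6 weeks".

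**Urine (Study Procedures, Day 0).** "The nurses will keep the daytime (7AM to 7PM) and nighttime (7PM to 7AM) urine separate to permit analysis of diurnal variation in urinary analytes". Under Day 1, the overnight collection is used for sodium and aldosterone.

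**Blood pressure.** Nocturnal BP from the 24-hour monitor is a listed outcome in Specific Aims. The monitor is fitted before discharge, worn for the next 24 hours, and "programmed to record the BP every 30 minutes during the day and every 60 minutes at night" (Devices to be used).

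**Morning tests (Study Procedures, Day 1).** Central BP is at 8:00AM, renal plasma flow testing at about 9:00AM, and the mixed meal follows.

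**Rationale.** Preliminary Work notes that "exposure to light at night during shift work depresses nocturnal melatonin secretion". Specific Aims names sleep restriction and desynchronization from shift work as separate disturbances, and the hypothesis to be tested concerns sleep restriction.

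**The concern.** The trial enrols people whose problem is meant to be too little sleep, and treats them with an extra hour of sleep with or without melatonin. Someone who works every night and sleeps by day may also be short of sleep, but has a second disturbance, misalignment with the clock, which an extra hour in bed does not address. Table 5 keeps out rotating night workers and says nothing about fixed ones.

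The procedures then treat everyone as a night sleeper. No passage shifts the dosing time, the urine windows or the BP night period to the individual's own sleep period. At stake is whether nocturnal BP and the day/night urine values mean the same thing in every participant. The Biostatistical analysis section says the pilot exists to supply means, standard errors and effect estimates for a larger trial, so avoidable variance here would carry into that design.

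**Working it through.** The plan gives no figure on this point to reproduce. The check is a reading of the criteria against the procedures, with simple arithmetic for scale.

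**1. Is the person eligible?** Take a fixed night worker who sleeps 6 hours by day and can add an hour. Of the items in Table 5 that touch sleep or schedule:
- Under 7 hours of sleep: met.
- Inability to extend sleep: does not apply.
- Rotating night shifts: does not apply, because the shift is fixed.
- Time-zone travel, insomnia, apnea, hypnotics, sleep aids: do not apply.

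The screening visit applies Table 5 only. Actigraphy and a sleep log run for 2 weeks before baseline, but no rule uses them to decide eligibility. No written criterion excludes this person.

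**2. Do the procedures fit?** The sleep times below are assumptions; the documents give none.

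| Assumed sleep | Hours inside 7PM–7AM |
|---|---|
| 23:00–05:00 | 6 of 6 |
| 08:00–14:00 | 0 of 6 |
| 09:00–15:00 | 0 of 6 |

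- Dosing: with bedtime at 08:00 or 09:00, one hour before bed is 07:00 or 08:00, which is not evening. The two parts cannot both be met.
- Urine: none of the usual sleep period lies in the night-time collection.
- Ambulatory BP: the monitored night follows discharge, so it can be a work night.
- Day 1: tests from 8:00AM onward fall in usual sleep time.

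**3. Weight of one participant.** The documents give both 8 per arm (Subject Enrollment; Biostatistical analysis) and 10 per arm (Potential Benefits).
- 1/8 = 12.5%
- 1/10 = 10%

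**4. Effect on a level.** Assume a clock-night dip of 10% in night sleepers and −10% in a day sleeper, a full inversion. With k day sleepers in an arm of N, the arm mean dip is [10(N − k) − 10k]/N.

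| N | k = 1 | k = 2 |
|---|---|---|
| 8 | (70 − 10)/8 = 7.5% | (60 − 20)/8 = 5.0% |
| 10 | (90 − 10)/10 = 8.0% | (80 − 20)/10 = 6.0% |

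**5. Effect on a change.** The plan compares changes from baseline. If the person keeps the same schedule at both visits, part of this offset cancels. It does not cancel if one monitored night is a work night and the other is slept through. Assuming awake SBP of 120 mmHg and a 10–15% dip, the spurious individual change is 120 × 0.10 = 12 to 120 × 0.15 = 18 mmHg. In an arm of 8 that moves the mean nocturnal change by 12/8 = 1.5 to 18/8 = 2.25 mmHg. This is an unfavourable case resting on several assumptions, not an expected value.

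**The case against.** Much of the case on the other side stands, and it limits the point.

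- **Intent.** Sleep is counted per night, participants extend nightly sleep, and drug is taken in the evening. Together these describe night sleepers, and a screener taking a history might well turn a day sleeper away. That is plausible, but no written rule requires it.
- **Few outcomes are split by day and night.** The five powered outcomes (renal plasma flow response to captopril, central BP, 24-hour mean SBP, insulin sensitivity, beta-cell response) are not. Specific Aims lists aldosterone as a 24-hour excretion. The labelling problem is confined mainly to nocturnal BP and the urine split, although the Day 1 morning tests would still be done at an unusual circadian time for this person.
- **Labels.** The urine windows are accurate as clock windows, and the monitor settings are a recording frequency. The documents do not say how nocturnal BP is derived. The difficulty is what the values mean in a day sleeper, not a false label.
- **Noise, not bias.** Allocation is random and the two inpatient visits are nearly identical, so such a participant adds variance rather than an expected difference between arms.

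Two stronger readings are tempting. A reader might infer that the plan contradicts its own logic by excluding time-zone travel and rotating shifts but not fixed nights. The documents do not support that: travel and rotating shifts are both unstable schedules, no reason is given for the travel exclusion, and the proteinuria study cited for shift work concerned rotating workers. A reader might also set the 1.5 to 2.25 mmHg shift beside the 3 and 6 mmHg in Table 7. Those figures concern 24-hour BP, and a 24-hour mean takes in the sleep period whenever it falls. They are not a benchmark for nocturnal BP, and the documents give no SD or detectable difference for it.

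**Conclusion.** The gap in Table 5 is real as written: a fixed night worker sleeping under 7 hours by day meets the criteria, and the dosing instruction, overnight urine collection and clock-night BP do not fit that person. The consequence is extra variability and harder interpretation of nocturnal BP and the day/night urine measures, together with a mixing of circadian misalignment into a sample meant to represent habitual sleep restriction. It is not grounds for claiming systematic bias between arms or for discounting the 24-hour mean BP result.

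The firm size is the share of an arm: 12.5% of 8, or 10% of 10, for each such participant. The dip and mmHg illustrations depend on assumed sleep times, BP and dipping, and the documents give no basis for how many such people would enrol. In arms this small even one is worth preventing when prevention costs so little, so the change should be made.

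**What to change.** Reword the Table 5 exclusion to: *Job requires any night-shift work (fixed or rotating), currently or planned during the study*. Ask about it at the telephone pre-screen. Use the 2-week pre-baseline actigraphy and sleep log, which the protocol already collects, to confirm that the main sleep period is at night. Since randomization takes place before the baseline admission, read these records before assignment so that nobody is removed after it. The eligibility and dosing passages must be reconciled so that both assume the same sleep period; no dosing rule is proposed here.

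The cost is one line in Table 5, one pre-screen question and a look at data already in hand. The downside is a few more screen failures and results that do not apply to fixed night workers.

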Day 1 — The second 12-hour urine collection will conclude at 7:00AM on day 1 and will be used to measure excretion of sodium and aldosterone. At 8:00AM, central blood pressure and vascular compliance will be assessed, followed at approximately 9:00AM by measurement of renal specific RAAS activity via para-aminohippurate (PAH) renal plasma flow testing with captopril, and systemic RAAS will be measured by plasma renin activity (PRA), angiotensin II (Ang II) and urine aldosterone. Next the subject will receive a mixed meal (10kcal/kg, 45% carbohydrate, 15% protein, 40% fat, 1g/kg glucose) to be consumed in 15 minutes with blood draws at 0, 10, 20, 30, 60, 90 and 120 minutes from the time the meal had begun to be consumed. The mixed meal will achieve glucose of 1g/kg by using specific amounts of a Trutol drink; the amounts are based on the subject’s weight, **Table 6**. Plasma glucose, insulin and c-peptide will be measured in all 7 samples of blood. Finally the participant will be fitted with a Spacelabs 90207 ambulatory BP monitor prior to discharge to be worn for 24-hours.

Food Description	Amount	Measure	Energy	Glucose (g)	Protein (%)	Fat (%)	Carbohydrate (%)
Whole milk, Hood	70	gram	44.49		21.05	47.37	31.58
Egg, whole	117	gram	174.33		34.45	62.18	3.37
Butter	7	gram	50.19		0.46	99.5	0.03
SF peanuts, dry roasted	30	gram	175.5		15.09	71.2	13.71
Turkey sausage	30	gram	46.68		42.56	53.85	3.59
Trutol, glucose drink	323	gram	327.52	81.72	0	0	100
Total			818.71	81.72	14.18	40.78	45.04

Follow-up — During the study, subjects will be phoned weekly by a study coordinator to assess for compliance and potential side effects. [name] will call all subjects every 2 weeks to discuss difficulties encountered with their new sleep schedule, to recommend improvements and encourage compliance with the protocol.

Parameters Measured: At the inpatient visits, the following measurements will be made:

Renal Specific RAAS — The activity of the local kidney RAAS can be measured by examining the change in effective renal plasma flow (RPF) after oral captopril while in high sodium balance. Effective RPF is measured as clearance of para-aminohippuric acid, because PAH is cleared solely and nearly entirely by the kidney. The protocol to measure PAH clearance is performed with the participant supine, **Figure 5**.

Systemic RAAS — PRA and ang II levels will be measured on the first morning blood draw.

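### On the visible text, the baseline ambulatory BP night opens the sleep-extension period and the follow-up BP night falls after it, which may blur the pre-post change in nocturnal BP

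*Combined protocol and SAP*

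**What the plan says.** Specific Aims lists nocturnal BP, taken from a 24-hour ambulatory monitor, among the CKD risk factors to be assessed. Biostatistical analysis says the pilot should yield effect estimates for both sleep extension and melatonin for planning a larger trial, and it powers 24-hour systolic BP for a 6 mmHg change attributed to sleep extension.

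On timing, the protocol gives these statements:

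- Subject Enrollment: "Endpoints will be measured at both the baseline and 6-week inpatient visits".
- Study Procedures, Treatment assignments: every participant is asked to add an hour of sleep "during the 6 week period between inpatient visits".
- Study Procedures, Baseline and Follow-up inpatient visit: "Baseline and 6-week inpatient visits will be virtually identical", and "Each inpatient visit will begin at 4:00PM on Day 0 and end at 4:00PM on Day 1".
- Study Procedures, Day 1, as the last procedure: "Finally the participant will be fitted with a Spacelabs 90207 ambulatory BP monitor prior to discharge to be worn for 24-hours". Devices to be used adds that the participant goes home wearing the monitor and returns it by post.
- Study Procedures, Pre-admission: actigraphy runs "2 weeks prior to the baseline inpatient visit and for the 6 weeks between inpatient visits", 8 weeks in total, and participants keep a "daily sleep log during the 2 weeks preceding the baseline visit and 6 weeks preceding second visit".

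The visible text gives no first or last night of extension. Figures 1 and 2, which outline the pilot and the inpatient visits, are not shown.

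**The concern.** Both arms extend sleep, so the trial's only information on the effect of extension is the change from baseline to follow-up. For that change to be read as before versus end of course, the baseline measurement should precede extension and the follow-up measurement should be made while extension is still in force.

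The ambulatory recording is the one endpoint whose baseline measurement runs on past the baseline visit, into the period in which extension is requested. It is also the endpoint that depends most directly on how the participant slept on the recorded night. If the baseline night already includes some extension and the follow-up night does not, the pre-post contrast in nocturnal BP is blurred. An effect estimate carried into the design of the larger trial would be blurred with it. Because sleep on the follow-up BP night is not measured, the problem could not be examined afterwards.

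**Working it through.** The plan states no figure to reproduce here. The check is a timeline built from the stated clock times, followed by a count of readings.

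**Timeline**

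1. Each visit runs from 4PM Day 0 to 4PM Day 1. The monitor goes on before discharge and is worn for 24 hours, so its only night is the night of Day 1, at home.
2. Taken literally, the extension period runs from baseline discharge to the second admission: 42 days if six weeks are counted from discharge, 41 days if counted from admission to admission.
3. Overlap of each recording with that period, with the monitor fitted 0, 1 or 2 hours before discharge, under both ways of counting, and with night assumed to be 10PM to 7AM:

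| Recording | Hours inside the period | Night hours inside |
|---|---|---|
| Baseline | 22-24 of 24 | 9 of 9 |
| Follow-up | 0 of 24 | 0 of 9 |

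The follow-up recording starts 22-24 hours after the period closes, with one inpatient night in between. All six combinations give the same placement.

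**Sleep measurement.** Actigraphy is 2 + 6 = 8 weeks, which is the stated total and leaves nothing after the second visit. The sleep log stops before the second visit. The follow-up BP night is therefore covered by 0 of the 2 sleep measures. This holds however the extension period is read.

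**Share of readings affected.** The monitor is set to "record the BP every 30 minutes during the day and every 60 minutes at night". With an assumed night of *h* hours, night readings = *h* and day readings = 2 × (24 − *h*):

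| Night (assumed) | Night + day readings | Night share by count | Night share by time |
|---|---|---|---|
| 7 h | 7 + 34 = 41 | 17.1% | 7/24 = 29.2% |
| 8 h | 8 + 32 = 40 | 20.0% | 8/24 = 33.3% |
| 9 h | 9 + 30 = 39 | 23.1% | 9/24 = 37.5% |

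For nocturnal BP, all 7-9 night readings at each visit come from the one night in question. For the 24-hour mean, each 1 mmHg of error in the night contrast alone would move the result by about 0.17-0.23 mmHg by count, or 0.29-0.38 mmHg time-weighted. The plan does not say which averaging is used, and the 1 mmHg is only a unit for scaling.

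Part of the baseline recording precedes any extended night. With a 4PM start, bedtime at 10PM gives 6 × 2 = 12 earlier readings (12/41 = 29.3% to 12/39 = 30.8%). Bedtime at midnight gives 8 × 2 = 16 (16/41 = 39.0% to 16/39 = 41.0%). The start time and bedtimes are assumptions.

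**The case against.** The strongest reply is that the deciding evidence may be in the figures. The phrase that sets the extension period describes an interval loosely and fixes no boundary nights, and Figure 1 is captioned as showing sleep extension. The investigators may have treated the 24 hours after baseline discharge as part of baseline. This stands, and it limits the point to a literal reading of the visible text. Likewise, saying that endpoints are measured at the visits is natural shorthand for a device fitted there.

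The rationale also concerns weeks of extension, not a same-night effect. At worst, one night of requested extension out of about 42 is compared with a night roughly a day after a six-week course. That may still approximate near-untreated versus end of course. A reader might infer that the pre-post change does not estimate the extension effect at all. The documents do not support that: nothing in them shows that one night produces the effect, or that six weeks of effect vanish by the next night.

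The follow-up half of the problem is not peculiar to the monitor. On the same reading, the Day 1 central BP, renal plasma flow and mixed-meal tests at the second visit also fall after the period closes. This stands too. What is distinctive for ambulatory BP is the baseline recording inside the period, together with an unmeasured follow-up night.

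Finally, the specified analysis is the melatonin-placebo ANCOVA, and the pre-post change has no non-extended control in any case. Both are correct. The missing control is a separate limit that better timing would not remove.

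**Conclusion.** The point holds as a scheduling inconsistency that should be corrected, with medium confidence. On the visible text, the baseline BP night opens the extension period, the follow-up BP night falls after it, and sleep on the follow-up night is unrecorded. The pre-post change in nocturnal BP may therefore be a blurred before-versus-end-of-course contrast. The 24-hour mean is affected only in part.

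The size and direction of any bias cannot be derived from the documents; dilution is more plausible than loss of the contrast. The reading shares assume a 7-9 hour night. The placement of the nights assumes that the between-visit wording is taken literally and that the unseen figures do not say otherwise.

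Two further inferences should be resisted. The randomized comparison is not shown to be biased, because the timing is the same in both arms and should largely cancel. Nor can anything be concluded about study drug on either BP night, because the visible text gives no first or last dose relative to the visits and the figures may.

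**What to change.** Reconcile Subject Enrollment, the Study Procedures text (Treatment assignments, the inpatient visit description and Day 1) and the ambulatory monitor paragraph. State that the baseline 24-hour recording is completed before the extension period starts and that the follow-up recording is completed before that period ends. Extend actigraphy and the sleep log by one night to cover the follow-up recording. If the figures already set this order, repeat it in the text.

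If the timing is left as it is, report the ambulatory BP pre-post change with the caveat that the baseline night may include extension and the follow-up night may not.

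The cost is wording plus one more night of actigraphy and sleep log per participant. Moving the recording to before admission is not recommended. It would overlap the three-day salt supplement, for which Risks and Discomforts lists raised BP as a possible effect, and the home urine collection, and it would need extra fitting contacts. Nothing here bears on dosing.
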